8.5. Type and duration of the follow-up of subjects after adverse events

All AEs will be monitored by the Investigator until a satisfactory outcome is obtained (i.e. the event is resolved or the condition is unlikely to change or the subject is lost to follow-up). All clinical and biological examinations judged necessary by the Investigator will be continued until return to normal. The Investigator will provide the Sponsor with copies of all examination results and treatments linked to the follow-up of AEs.

8.6. PREGNANCY IN THE CLINICAL TRIAL

Prior to enrolment in the clinical trial, volunteers ‘partners with childbearing potential must be advised of the importance of avoiding pregnancy from the time of informed consent signature up to 90 days after the last IMP administration-and of the potential risks associated with an unintentional pregnancy.

A male participating to the study have to agree to use a condom with spermicide, on the time of informed consent signature, up to 90 days after the last IMP administration. The Principal Investigator or a delegate must inform a female sexual partner to use at least one of the following reliable methods of contraception:

- a. Hormonal oral, implantable, transdermal, or injectable contraceptives
- b. A non-hormonal intrauterine device [IUD] or female condom with spermicide or contraceptive sponge with spermicide or diaphragm with spermicide or cervical cap with spermicide

During the trial and within 30 days after the last IMP administration, female subjects are to be instructed to contact the Investigator immediately if they suspect they might be pregnant. In the same way, male subjects who become aware that the partner might be pregnant, are to be instructed to contact the Investigator immediately.

The Investigator must report every pregnancy on a pregnancy report form as soon as possible (within 24 hours of learning of the pregnancy to the Dompé Drug Safety contacts reported at Paragraph 8.4, even if no AE has occurred, and follow it to term. If, however, the pregnancy is associated with an SAE (eg, if the mother is hospitalized for an adverse event), in addition to the pregnancy report form, a separate SAE report form must be filed as described in Section 8.4 with the appropriate serious criterion (eg, hospitalization) indicated on the SAE report form. Miscarriage, stillbirth and any malformation/disease must be reported as a SAE.

A form prepared by Dompé will be utilized to capture all pregnancy-related information until the birth of the child.

8.7. OVERDOSE

Cases of overdose (accidental or intentional) which may or may not result in serious adverse reactions are to be reported to Sponsor Drug Safety, following the same procedure for SAE, within 24 hours from the Investigator's knowledge of its occurrence. This includes reports related to drug intake with suicidal intentions and consequent drug overdose.

Overdose, and shall be reported, even if not associated with adverse reactions, within 24 hours, in a SAE form, to Dompé PHARMACOVIGILANCE contacts reported at Paragraph 8.4 and to Dompé Medical Expert, who should be contacted to discuss corrective treatment, if necessary.

9. DATA MANAGEMENT

9.1. Definition of source data

All evaluations that are reported in electronic Case Report Form (eCRF) must be supported by appropriately signed identified source documentation related to but not limited to:

- Subject identification, last participation to a clinical trial, medical history, previous and concomitant medication;
- Physical examination, blood pressure and heart rate, body weight, BMI, subject habits;
- Dates and times of study drug administration;
- Pharmacokinetic time points;
- Laboratory assessments, meals;
- AEs.

9.2. Source document requirements

According to the guidelines on GCP, the Monitoring Team must check the eCRF entries against the source documents, except for the pre-identified source, data directly recorded/enclosed in/to the CRF. The Informed Consent Form will include a statement by which the subject allows the Sponsor's duly authorized personnel, the Ethics Committee, and the regulatory authorities to have direct access to source data which supports the data on the eCRF (e.g. subject's medical file, appointment books, original laboratory records, etc.). These personnel, bound by professional secrecy, will not disclose any personal identity or personal medical information.

9.3. Use and completion of the eCRF and additional request

9.3.1.1. Data collection

All clinical data will be reported electronically by the Investigator or authorised designee on a web-based eCRF. This eCRF is specifically designed for the study and developed by the Data Management Department of Eurofins Optimed using Viedoc version 4., a validated Electronic Data Capture system, 21 CFR Part 11 compliant.

Should a correction be made, the corrected information will be entered in the eCRF and the initial information will be tracked in the audit trail.

9.3.1.2. Responsibilities

The Investigator or authorised designee is responsible for the timeliness, completeness, and accuracy of all observations and other data pertinent to the clinical investigation in the eCRFs.

The Investigator will ensure that all data are entered promptly (within 2 days) after the evaluation has occurred, in accordance with source documents and specific instructions accompanying the eCRFs, designed specifically for the study.

The Data Management Department of Eurofins Optimed will provide all tools, instructions, and training necessary to complete the eCRF, and each user will be issued a unique username and password. The data management of Eurofins Optimed will be responsible for data processing, in accordance with the CRO data management procedures.

9.3.1.3. Data Management

During the study, through regular data collection and monitoring, clinical data will be reported in the eCRF. Computerised logic and/or consistency checks will be systematically applied in order to detect errors or omissions. Queries will be generated and submitted through the electronic data capture (EDC) system to the investigator sites for resolution (queries should be answered within 3 working days, except close to the database lock period, queries should be answered within 1 working day).

Correction will be made either automatically from the immediate completion or following the review of the data during the Eurofins Optimed monitoring. An audit trail, which will be initiated at the time of the first data entry, allows tracking all modifications.

The Data Management Department of Eurofins Optimed may generate additional requests to which the Investigator must respond electronically by confirming or modifying the data questioned. The requests with their responses will be implemented to the eCRFs.

Each step of this process will be monitored through the implementation of individual passwords and regular backups to maintain appropriate database access and to ensure database integrity.

When eCRFs are complete and all queries have been answered, the Investigator has to sign the eCRFs. Then eCRFs are locked and no modification is possible anymore.

After integration of all corrections in the complete set of data, the database will be locked and saved before being released for statistical analysis.

After database lock, a Patient Data Report (PDR) consisting of the creation of the entire casebook for a subject, including the audit trail, will be generated for each subject in .pdf format. The investigator and the Sponsor will receive the PDRs for archiving after the lock of the database. All Data Management activities will be described in a document, the Data Management Plan.

9.4. Study monitoring

EUROFINS OPTIMED will perform the study in accordance with this protocol, GCP and the applicable regulatory requirements and the contract with the Sponsor.

The Investigator is required to ensure compliance with the Investigational Product schedule, visit schedule and procedures required by the protocol. The Investigator agrees to provide all information requested in the CRF in an accurate manner according to the instructions provided and to ensure direct access to source documents to Sponsor representatives.

The Sponsor is responsible to Health Authorities for taking all reasonable steps to ensure the proper conduct of the study as regards ethics, protocol compliance, integrity and validity of the data recorded on the Case Report Forms. Thus, the main duty of the Monitoring Team is to help the Investigator and the Sponsor maintain a high level of ethical, scientific, technical and regulatory quality in all aspects of the study.

9.5. Access to data by the subjects

In conformity with the law, any subjects who so wish may access any data concerning them, at the end of the research. They should address their request in writing to the Investigator, and will obtain a response within 8 working days.

10. STATISTICS

10.1. Description of the statistical methods

The statistical analysis will consist in individual data listings and descriptive statistics performed by EUROFINS OPTIMED, using the SAS® computer program (release 9.3).

All individual data for all included subjects will be presented in data listings, sorted by subject within study product/treatment group.

Demographic and baseline characteristics data will be summarized by product/treatment, cohort and visit day where consistent.

For parameters with evaluation before dosing and in case of rechecked value(s) for one subject, only the last observation will be used in descriptive statistics and derivations of other parameter values. After dosing, only observations planned in the protocol will be used in descriptive statistics.

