3.5.2. Stopping rule for a subject

During the treatment period, the safety and tolerability will be evaluated on an ongoing basis, the following criteria will apply to stop a subject:

- The subject experiences an AE that prevents him from continuing in the study,
- Significant increase (i.e. $> 3N$) of ALT (N being the upper limit of the normal value),
- Abnormal laboratory results with simultaneous increases of total bilirubin ($> 2 N$), ALT ($> 2 N$) and alkaline phosphatases ($> 1.5 N$),
- The subject develops a serum creatinine ≥ 2 times the ULN,
- Sustained QTcF value of > 500 msec confirmed by at least one repeat ECG,
- The subject withdraws consent,
- At the request of the Sponsor or at the Investigator's request (for example if the Investigator considers that the subject's health is compromised by remaining in the study or the subject is not sufficiently cooperative).

See also Section 3.6 "Removal of Subjects from Therapy or Assessment".

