10.5. Procedure for accounting, for missing, unused, and spurious data

Missing data values will not be replaced.

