3 STATISTICAL ELEMENTS

The statistical analysis performed by EUROFINS OPTIMED pertains to description at baseline, conduct of the study and safety analysis with statistical software SAS (version 9.4).

The pharmacokinetic statistical analysis will be performed by PhinC Development.

The Correlation analysis between pharmacokinetic and pharmacodynamic parameters will be performed by EUROFINS OPTIMED.

Interim analysis: For each part of the study, an interim PK analysis on DF2577Y (the acid form of DF2755A) and its metabolites (if any) will be performed after completion of each dose level. This analysis will be done on anonymized data provided by the bioanalytical center to prevent any violation of the double blind condition of the study.

Final PK analysis will be performed using final validated bioanalytical data and actual PK blood sampling times.

For safety parameters (laboratory safety parameters, vital signs, ECG), in case of repeat assessments, the last assessment prior to the administration of the study treatment and the first assessment after the administration will be used for descriptive statistics. All assessments, including the repeat assessment will be included in the data listings and will be flagged accordingly.

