4.5 Safety: Laboratory criteria

The objective of analysis presented below is to evaluate the safety laboratory variables.

Biochemistry, hematology and hemostasis criteria

Criteria	
	Biochemistry Creatinine (μmol/L) Glucose (mmol/L) Total protein (g/L) Urea (mmol/L) Albumin (g/L) Globulin (albumin/globulin ratio) Total cholesterol (mmol/L) Triglycerides (mmol/L) Sodium (mmol/L) Potassium (mmol/L) Chloride (mmol/L) Calcium (mmol/L) Uric acid (IU/L) AST (IU/L) ALT (IU/L) GGT (IU/L) Alkaline phosphatase (IU/L) CPK (IU/L) Total bilirubin (μmol/L) Conjugated bilirubin (μmol/L) LDH (IU/L) LDL (mmol/L) HDL (mmol/L) Phosphore (mmol/L) Hematology Hemoglobin (g/L) Hematocrit (no unit) Red blood cells (Tera/L) White blood cells (Giga/L) Neutrophils (Giga/L) Eosinophils (Giga/L) Basophils (Giga/L) Lymphocytes (Giga/L) Monocytes (Giga/L) Platelets (Giga/L) Reticulocytes (Giga/L) MCV (fL) MCH (fmol) MCHC (mmol/L) Hemostasis aPTT subject (s) aPTT ratio Prothrombin time (s) Prothrombin level

Information	
Part A: criteria assessed at screening, D-1, D2 and at end of study visit (D4.).
 
Part A, baseline: last assessed value at D-1.
 
Emergent value is defined as any normal value at pre-dose assessment (baseline value) according to laboratory range becoming abnormal at post-dose assessment or lower (upper) abnormal baseline value becoming upper (lower) abnormal at post-dose assessment.
 
Laboratory ranges are reported in database.

Population	SS.
Statistical method	
For each criterion
 
Values, position according to laboratory range and clinical assessment will be described at screening, baseline, each scheduled assessment during treatment phase and at end of study visit overall.
 
Change between the values from baseline to each scheduled assessment during treatment phase and end of study visit will be described by dose group and overall.
 
Listing of emergent values according to laboratory range from Baseline to each scheduled assessment during treatment phase and end of study visit by dose group and subject.

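### The size of an unscheduled or follow-up laboratory, vital-sign or ECG peak enters no numeric safety summary by dose group, and no table counts subjects who cross the protocol's own limits

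*Protocol*

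**What the plan says.** The primary criteria are adverse events, vital signs, ECG and laboratory tests (Protocol 3.1.1). Four rules decide which of the measured values reach a table.

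- Protocol 10.1: "After dosing, only observations planned in the protocol will be used in descriptive statistics".
- SAP section 3, for repeated laboratory, vital-sign and ECG assessments: "the last assessment prior to the administration of the study treatment and the first assessment after the administration will be used for descriptive statistics". The other values go to the listings: "All assessments, including the repeat assessment will be included in the data listings and will be flagged accordingly".
- SAP 4.5, 4.6 and 4.8: tables by scheduled visit, plus an emergent-value output on the same basis. For laboratory data this is a "Listing of emergent values according to laboratory range from Baseline to each scheduled assessment during treatment phase" and to the end-of-study visit.
- Protocol 10.5: "Missing data values will not be replaced".

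Two other sections generate values outside the schedule, or gaps within it. Protocol 3.5.2 lists individual limits (ALT, a bilirubin/ALT/alkaline phosphatase combination, creatinine, QTcF) and says that "the following criteria will apply to stop a subject". Protocol 8.5 says: "All clinical and biological examinations judged necessary by the Investigator will be continued until return to normal".

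**The concern.** The protocol judges safety on individual extremes. A subject stops on a multiple of the ALT or creatinine limit or on a confirmed QTcF value, and escalation stops when two subjects cross such limits (3.5.4). The planned tables describe something else: the distribution of values at fixed times. Extra tests are done mainly because a value is already abnormal, so the measurements left out of the tables are the ones most likely to hold the peak.

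In Part B a second mechanism acts. A subject stopped for a raised value has no planned observations until the end-of-study examination, and nothing replaces them. The visit means in between describe only subjects who did not have the problem. A reader of the dose-group tables could then understate how large a change occurred, or how many subjects crossed a limit at any time.

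**Working it through.** No figure in the plan can be reproduced here: no sample size was calculated, and the SAP makes the safety analysis descriptive. The check is arithmetic on one subject's contribution to a dose group.

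**Inputs from the documents.** Active subjects per cohort: 6 in Part A, 9 in Part B (Protocol 1.6). Male ALT upper limit: 42 U/L (laboratory ranges attached to the SAP). Planned post-dose laboratory days: D2 and D4 in Part A (SAP 4.5); D5, D7, D10, D14 and D17 in Part B (Protocol 8.2.2).

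**Assumptions.** Baseline ALT 25 U/L (range 15 to 35); all other subjects unchanged; one subject with a planned value of 1.5 times the limit and an unscheduled peak of 5 times the limit.

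**Unscheduled peak.** Planned value 1.5 × 42 = 63 U/L; peak 5 × 42 = 210 U/L.

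| Statistic (U/L) | Planned values only | Worst post-dose value |
|---|---|---|
| Maximum change | 63 − 25 = +38 | 210 − 25 = +185 |
| Mean change, n = 6 | 38/6 = +6.3 | 185/6 = +30.8 |
| Mean change, n = 9 | 38/9 = +4.2 | 185/9 = +20.6 |

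With a baseline of 15 the maximum changes are +48 and +195; with 35 they are +28 and +175. The gap is 210 − 63 = 147 U/L whatever the baseline.

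**Stopped subject, Part B.** Suppose the value of 210 U/L is found at the planned D7 draw and the subject is stopped.

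1. At D7 the value is tabulated: mean change (210 − 25)/9 = +20.6 U/L (19.4 to 21.7 over the baseline range), and the maximum shows 210.
2. At D10 and D14 the subject is missing. The other eight are flat by assumption, so the mean change is 0.
3. At the end of study the subject is examined again (Protocol 4.5.1), but neither document says whether an early examination is tabulated in the D17 row.

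The ALT criterion requires more than 3 × 42 = 126 U/L, so any male subject who meets it adds more than (126 − 25)/9 = 11.2 U/L to the mean at the visit where it is seen.

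**Threshold counts.** The SAP tables give position against the normal range at each scheduled time. Protocol 10.1.2.2 adds potentially significant vital-sign and ECG abnormalities, also at scheduled times. Neither gives the number of subjects who crossed a 3.5.2 or 3.5.4 limit at any post-dose time.

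**The case against.** A reader might infer that such a peak disappears from every summary, that stopped subjects leave only blanks, that the group mean falsely returns to baseline, and that the bias always favours the drug. The documents do not support these readings.

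- Protocol 8.3.1 makes an abnormality an adverse event if it is symptomatic, clinically significant or leads to discontinuation. It then enters the treatment-emergent output (SAP 4.4). SAP 4.9 also tabulates withdrawal reasons by dose group, with a category for adverse laboratory findings.
- SAP 5 lists unscheduled evaluations. For biochemistry, haematology and urinalysis it carries an emergent flag at each assessment.
- Stopped subjects have the end-of-study examinations, so only the visits in between are blank.
- The first-assessment rule usually keeps the abnormal value that prompted the recheck, and prevents a normal repeat from overwriting it.
- The tables show N and the maximum (Protocol 10.1.1). An asymptomatic rise is normally first seen at a planned draw, so that first value is tabulated.
- Escalation reviews individual out-of-range results (3.3.3.2), not visit means. The blank-visit argument concerns Part B, whereas this SAP details only Part A.

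All of this stands and limits the point. What it leaves open is size and frequency. The adverse-event table counts events and subjects without the magnitude of the change, and gives way to a listing when there are five or fewer events. A falling N is an imperfect warning, because Protocol 4.5.2 has treated subjects who end early replaced. Listings hold every value, but they are not a dose-group summary of a primary criterion.

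**Conclusion.** The point holds as a gap in the planned summaries that is cheap to close. The size of an unscheduled or follow-up peak is outside every numeric laboratory, vital-sign and ECG summary by dose group, in both parts, and no table counts subjects crossing the protocol's own limits. In Part B, later visit means can look more normal than the experience of all dosed subjects. This is possible, not certain: it requires the remaining subjects to be near baseline, and it need not last to the end-of-study row.

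The figures of +38 against +185 U/L are an illustration. They rest on the assumed baseline, the assumed planned and peak multiples, and flat values in the other subjects; they do not predict what the trial will show. The documents do not support a finding that the signal is lost or that the tables are wrong for what they describe.

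**What to change.** Keep the by-visit tables with their planned-observation and first-assessment rules, which stop frequently retested subjects from dominating a visit. Then:

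1. For each dose group and placebo, add per-subject worst post-dose value, change and shift from baseline for key laboratory, ECG and vital-sign parameters, using all post-dose values (scheduled, unscheduled, repeat, follow-up, early termination). For blood pressure and heart rate, give both highest and lowest.
2. On the same data, add counts of subjects crossing the limits already written in Protocol 3.5.2 and 3.5.4.
3. Extend the emergent-value listing to unscheduled ECG and vital-sign assessments; SAP 5 lists these without an emergent flag.
4. State in which row an early end-of-study examination is tabulated.

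State in Protocol 10.1 that the planned-observation rule applies to the by-visit tables only. Apply the changes to Part A and to the Part B analysis plan. Missing visits need no imputation.

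The cost is some SAP wording and a few extra tables from data already collected. The downside is that subjects measured more often tend to have more extreme worst values; a footnote giving the number of assessments per subject deals with this.

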10.1.1. Descriptive statistics

Descriptive statistics for quantitative parameters will be provided using mean, Standard Deviation (SD), Standard Error of the Mean (SEM), minimum, median, maximum, and number of observations; descriptive statistics for qualitative parameters will be provided using frequencies (n) and percent frequencies (%). Percent will be calculated using as denominator the actual number of non-missing data.

10.1.1.1. Subject demographic characteristics, medical history and diagnoses

Continuous variables (age, height, weight, BMI and qualitative variables (race) will be summarized in descriptive statistics on the included subjects and/or pharmacokinetic population, if relevant.

Medical history will be listed and summarized by system organ class and preferred term, if relevant (Medical Dictionary for Regulatory Activity (MedDRA)). Abnormal physical findings at baseline will be listed.

10.1.1.2. Previous medications

Previous medications will be coded according to the World Health Organization-Drug Reference List (WHO-DRL). Subjects who took medications that were stopped before the first study drug dosing will be listed.

10.1.1.3. Baseline safety parameters

Individual safety data (clinical laboratory, vital signs) measured before the first drug administration will be checked for validity of entrance criteria, and abnormalities will be documented. Individual abnormalities before dosing will be flagged in data listings and presented along with post-dose measurements in the statistical appendices.

